The secondary objectives of this study will assess whether our Fiasp® intervention is superior to NovoLog® in terms of postprandial glucose control (time spent in SG target range of 100-180 mg/dL in all of the 4 hour postprandial periods).

We will also assess glycemic control during other time periods during the study, and examine differences in hyperglycemia and hypoglycemia between groups. We will also analyze glucose variability and differences in insulin dosing between groups. All glycemic outcomes will be assessed using data obtained from CGM.

Secondary outcomes will include:

- 1. Percentage of time spent in the glycemic target range of 100-180 mg/dL (both inclusive) during the duration of the study.
- 2. Percentage of time spent in the glycemic range of 70-140 mg/dL (both inclusive) in all of the 4 hour postprandial periods.
- 3. Percentage of time spent in nocturnal glycemic target range 100-180 mg/dL (both inclusive) during the nocturnal period (00:01 AM to 05:59 AM, both inclusive)
- 4. Percentage of time spent with hypoglycemia (<70 mg/dL, <54 mg/dL, and <40 mg/dL respectively) in all of the 4 hour postprandial periods, in the nocturnal period (00.01 AM to 05:59 AM, both inclusive), and during the combined period of sensor wear during the study.

- 5. Percentage of time spent with level 2 hyperglycemia (>240 mg/dL) in all of the 4 hour postprandial periods.
- 6. Percentage of time spent with level 1 hyperglycemia (181-239 mg/dL, both inclusive) in all of the 4 hour postprandial periods.
- 7. Mean SG glucose concentrations during the study.
- 8. Glucose variability as measured by standard deviation (SD) of glucose and coefficient of variation (CV).
- 9. Comparison of basal, prandial and correction insulin doses.

10. Patient reported adverse effects from wearing a CGM and their perception of the experience of wearing a CGM while in the hospital.

Study Duration

24 months: 18 months for recruitment, 6 months for analysis.

Study Design

Open-label, 1:1 randomization without placebo control.

Study Population

Inclusion criteria:

- 1. English-speaking or Spanish-speaking
- 2. Males and female adult subjects admitted to Boston Medical Center to a medical or surgical floor.
- 3. Age \geq 21 and \leq 80 years.
- 4. Diagnosed with type 2 diabetes at least 180 days prior to screening.
- Hyperglycemia during admission, as defined by a point of care and/or venous blood glucose ≥ 140 mg/dL.

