4.3 Secondary Objectives

The secondary objectives of this study will assess whether our Fiasp® intervention is superior to NovoLog® in terms of postprandial glucose control (time spent in SG target range of 100-180 mg/dL in all of the 4 hour postprandial periods).

We will also assess glycemic control during other time periods during the study, and examine differences in hyperglycemia and hypoglycemia between groups. We will also analyze glucose variability and differences in insulin dosing between groups. All glycemic outcomes will be assessed using data obtained from CGM.

Secondary outcomes will include:

- 1. Percentage of time spent in the glycemic target range of 100-180 mg/dL (both inclusive) during the duration of the study.
- Percentage of time spent in the glycemic range of 70-140 mg/dL (both inclusive) in all of the 4 hour postprandial periods.
- 3. Percentage of time spent in nocturnal glycemic target range 100-180 mg/dL (both inclusive) during the nocturnal period (00.01 AM to 05:59 AM, both inclusive)

- Percentage of time spent with hypoglycemia (<70 mg/dL, <54 mg/dL, and <40 mg/dL respectively) in all of the 4 hour postprandial periods, in the nocturnal period (00.01 AM to 05:59 AM, both inclusive), and during the study.
- 5. Percentage of time spent with level 2 hyperglycemia (>240 mg/dL) in all of the 4 hour postprandial periods.
- 6. Percentage of time spent with level 1 hyperglycemia (181-239 mg/dL, both inclusive) in all of the 4 hour postprandial periods.
- 7. Mean SG glucose concentrations during the study.
- 8. Glucose variability as measured by standard deviation (SD) of glucose and coefficient of variation (CV).
- 9. Comparison of basal, prandial and correction insulin doses between the two groups.
- 10. Patient reported adverse effects from wearing a CGM and their perception of the experience of wearing a CGM while in the hospital.

5 – Study Design

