Blood glucose levels will be monitored and insulin will be dosed using the standard hospital point-of-care glucose meters (Accucheck Inform II[™] meter). This is standard for use in the hospital to monitor glucose and adjust insulin. The CGM data will not be visible to the subject, nurse, or study team in real time, but will be retrospectively downloaded to assess outcomes for the study. Current BMC practice aligns with that of other hospitals in the United States, which may allow patients to wear continuous glucose monitors in the hospital, however does not use them to make insulin dosing decisions. There have been some studies evaluating the accuracy and utility of CGM devices in non-critically ill patients (14, 15). These studies have not found a significant difference in mean hospital glucose when comparing to data obtained by point-of-care meters, but have shown a greater ability to detect hypoglycemia.

On the day of enrollment and after obtaining informed consent, the Dexcom G6 Pro CGM sensor will be placed in the afternoon, with the insulin protocol to be started with basal insulin that evening at bedtime and the meal insulin dosing to begin the next morning. Each individual subject will have CGM data for a minimum of 4 and maximum of 6 meals during the study, unless the CGM sensor needs to be removed as described per protocol.

Insulin doses will be titrated daily as per insulin titration protocol (Appendix 2).

Subjects would continue in the study until discharge, or would be withdrawn if transferred to a higher acuity level of care, if nutrition method was changed, or after the subject has received 4-6 meal doses within the 72 hours of active sensor wear time (3 days). If a subject does not receive the minimum 4 meal doses during the 72 hours, the sensor wear period may be extended up to an additional 48 hours in order to successfully complete the study.

Subjects will be educated to avoid unscheduled eating to prevent potential hyperglycemic events at the time of enrollment and additionally if needed.

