5.1.1 Study Date Range and Duration

From the date of first subject screening, we plan to consent 210 subjects, randomize 178 subjects (89 per group) to achieve our target of 160 subjects (80 per group) who complete the study, over a period of 18 months. See section 6.7.3 for detailed power calculations. The active sensor wear time per subject will be 48-72 hours and maximum allowed active sensor wear time can be extended and additional 48 hours if needed to successfully complete the study. In the subsequent 6 months, the study team will analyze collected data and prepare for publication.

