6.3.6 Statistical Design

The design is a randomized, open-label study. In order to reduce bias we propose stratified randomization per ward, whereby separate randomization lists will be developed for each individual ward.

The Dexcom G6 Pro CGM sensor will store four measurements per hour. If each subject remains in the study after sensor placement for a minimum of 48 hours, each subject will have 192 glucose measurements and a minimum of 4 postmeal periods of data. We will discard data from the first 12 hours after sensor placement given concerns about data accuracy during this time period, leaving a minimum of 144 measurements/subject. As the CGM will be placed the afternoon prior to starting the prandial insulin dosing, we anticipate that discarding the first 12 hours of data will have minimal impact on the study.

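### Nocturnal and whole-study secondary outcomes include first-night readings taken before the first study meal dose, which can pull differences between the arms toward zero

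*Combined protocol and SAP*

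**What the plan says.** Section 5.1 places the sensor on the afternoon of enrollment, after consent and randomization, "with the insulin protocol to be started with basal insulin that evening at bedtime and the meal insulin dosing to begin the next morning". Both arms receive insulin glargine. They differ in the rapid-acting insulin, which is used for meals and for correction, including a correction scale at bedtime.

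Section 6.3.6 states "We will discard data from the first 12 hours after sensor placement given concerns about data accuracy during this time period". It expects little impact from this because meal dosing has not yet begun.

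The windows for the outcomes outside the postprandial periods are set by clock time or by study duration. Section 4.3 measures hypoglycemia "in the nocturnal period (00.01 AM to 05:59 AM, both inclusive), and during the study", besides the postprandial periods. The Synopsis gives the last of these as "during the combined period of sensor wear during the study". Outcome 1 (time in range) and outcome 7 (mean glucose) run over the study, and outcome 3 uses every nocturnal period. Outcome 8 (SD and CV) has no stated window.

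Section 6.3.7.1 computes percent time as readings in range over all recorded readings. No section restricts any of these windows to time after the first study meal dose. The first-three-meals sensitivity analysis in 6.3.7.2 is meant to address length of stay and does not state such a restriction.

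**The concern.** Section 5.1 presents the meal-time rapid-acting insulin as the intervention. Readings taken before its first dose carry little or no information about the comparison, yet they count in full in both numerator and denominator. If the true difference appears only after meal dosing starts, averaging in earlier time pulls the estimate toward zero.

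The matter is most important for nocturnal hypoglycemia. Each participant contributes few nights, so one partial night before meal dosing can be a large fraction of the total, and attenuation there could hide a safety difference. The fraction also varies with placement time and length of wear, so participants contribute unequal mixtures of time before and after the first meal dose.

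**Working it through.** **The plan's own counts.** "The Dexcom G6 Pro CGM sensor will store four measurements per hour", so 48 h × 4 = 192 readings. After the discard, (48 − 12) × 4 = 144, which agrees with "leaving a minimum of 144 measurements/subject".

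**Inputs from the documents.** Afternoon placement; 12 h discarded; meal dosing from the next morning; nocturnal window 00:01-05:59, taken as 6 h. On wear time, Section 5.1.1 says "The active sensor wear time per subject will be 48-72 hours", extendable by 48 h.

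**Assumed inputs.** The documents give no clock time for placement or for breakfast. I take placement at 13:00-17:00 and the first study meal dose at 08:00.

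**Formulas.** For placement at hour P:
- Retained data begin at P + 12 − 24 on the first night, that is at P − 12.
- First-night nocturnal hours = 6 − (P − 12).
- Nocturnal share = first-night nocturnal hours ÷ (those hours + 6 per later night). There is one later night at 48 h and two at 72 h.
- Overall share = [8 − (P − 12)] ÷ (wear − 12).

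| Placement | Retained from | Nocturnal share, 48 h | Nocturnal share, 72 h | Overall share, 48 h | Overall share, 72 h |
|---|---|---|---|---|---|
| 13:00 | 01:00 | 5/11 = 45% | 5/17 = 29% | 7/36 = 19% | 7/60 = 12% |
| 15:00 | 03:00 | 3/9 = 33% | 3/15 = 20% | 5/36 = 14% | 5/60 = 8% |
| 17:00 | 05:00 | 1/7 = 14% | 1/13 = 8% | 3/36 = 8% | 3/60 = 5% |
| 18:00 | 06:00 | 0 | 0 | 2/36 = 6% | 2/60 = 3% |

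**Sensitivity.** Moving breakfast by an hour shifts the overall share by 1/36 (about 3 points) at 48 h or 1/60 (about 2 points) at 72 h. It leaves the nocturnal share unchanged. If wear is extended to 120 h, placement at 13:00-17:00 gives 5/29 to 1/25 = 17-4% of nocturnal readings and 7/108 to 3/108 = 6-3% of all readings.

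**Effect on a difference.** Let s be the share before the first meal dose, D the arm difference after it and d the difference before it. For percent time or mean glucose, the expected difference is (1 − s)D + sd. With d = 0 this is (1 − s)D, a shrinkage of s. If first-evening correction gives d the same sign as D, the shrinkage is smaller. SD and CV are not time averages, so the formula does not apply to them.

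**Illustration on the plan's scale.** Section 6.3.7 uses 20 mg/dL, SD 45 mg/dL and 80 per group, for which power is 0.80. Suppose 20 mg/dL were the difference after the first meal dose, d = 0 and the SD were unchanged. With placement at 14:00:
- 48 h wear: s = 6/36 = 16.7%, diluted difference 16.7 mg/dL, power 0.65.
- 72 h wear: s = 6/60 = 10%, diluted difference 18.0 mg/dL, power 0.72.

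**The case against.** Counting all retained sensor time is a defensible choice. The hours are post-randomization and both arms are handled alike, so neither arm is favoured. This stands: the issue is attenuation and precision, and no bias toward one product arises.

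A reader might infer that the first night is untreated. The documents do not support that. Glargine is given at bedtime on the day of entry. Section 5.1 also gives bedtime correction in the assigned insulin when glucose is 200 mg/dL or more, and Appendix 1 allows an additional 2 AM correction scale for some patients. Whether these apply on the enrollment evening is not stated: Section 5.1 says the insulin protocol starts then but names only basal insulin. A zero arm difference on the first night is therefore an assumption, and the shares above are approximate upper figures for the shrinkage. It also follows that moving every window to the first meal dose could delete hypoglycemia that follows a first-evening correction dose.

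Re-anchoring has a further cost. With placement at 14:00, nocturnal data fall from 10 h to 6 h at 48 h wear, and anyone who leaves before the second night has no nocturnal value. Fewer readings make each participant's percentage noisier, so a net gain in power has not been shown.

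The size depends on assumed clock times, is largest at the shortest wear, and is zero for the nocturnal outcomes if placement is at 18:00 or later. Section 3.2.1 also plans to analyse the number of hypoglycemic episodes; extra common time adds noise to a count but does not shrink the absolute difference.

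**Conclusion.** The point holds for outcomes 1, 3 and 7 and for the nocturnal and whole-study parts of outcome 4. It extends to outcome 8 only if SD and CV are computed over all sensor wear, and there the shrinkage is not proportional. As written, these outcomes include first-night time before the first study meal dose, when the arms differ only if the assigned insulin was given as correction that evening.

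Under the assumed times, differences in percent time and mean glucose are attenuated by at most about 14-45% (nocturnal) and 8-19% (whole study) at 48 h wear, or 8-29% and 5-12% at 72 h. This bound assumes that any first-night difference does not run in the opposite direction.

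Two stronger inferences should be resisted. The primary outcome, the superiority objective and the postprandial secondary outcomes use only the 4-hour postprandial periods and are not affected. The 80 per group is not in error either: Section 6.3.7 bases it on day-2 mean glucose, not whole-study mean glucose, so the reduced power figures are illustrations only.

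**What to change.** In Sections 4.3 and 6.3.7.2, and in the matching Synopsis list:

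- Start the nocturnal and whole-study efficacy windows at the first study meal dose. The first night counted is then the one after the first study dosing day.
- State the window for SD and CV.
- Report the first-night readings descriptively.
- For hypoglycemia, also report all retained post-randomization sensor time, or time from the first dose of assigned rapid-acting insulin including any first-evening correction.
- Keep the all-sensor-time analysis as a sensitivity analysis.
- Reconcile the passages in Section 5.1 so that it is clear whether the correction scales operate on the enrollment evening.

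This changes definitions only and needs no new data. The cost is less data in the main version of these outcomes. With placement at 14:00 and a first dose at 08:00, 48 h wear leaves 30 h (120 readings) instead of 36 h (144), and 6 h of nocturnal data instead of 10 h. At 72 h wear it leaves 54 h instead of 60 h, and 12 h of nocturnal data instead of 16 h. Participants who leave before the second night would have no nocturnal value in that version; their number should be reported by arm.

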5.1.1 Study Date Range and Duration

From the date of first subject screening, we plan to consent 210 subjects, randomize 178 subjects (89 per group) to achieve our target of 160 subjects (80 per group) who complete the study, over a period of 18 months. See section 6.7.3 for detailed power calculations. The active sensor wear time per subject will be 48-72 hours and maximum allowed active sensor wear time can be extended and additional 48 hours if needed to successfully complete the study. In the subsequent 6 months, the study team will analyze collected data and prepare for publication.

5.1.2 Number of Study Sites

Single site — Boston Medical Center

5.2 Primary Outcome Variables

All SG values collected by CGM during the postprandial study period.

5.2.1 Secondary and Exploratory Outcome Variables

All SG values collected by CGM during the hospital stay, analyzed as detailed above in Section 4.3 of the Study Objectives. Insulin doses given in each group will be analyzed. Demographic information including age, sex, race, BMI, reason for hospitalization, creatinine, HbA1c and medications prior to hospitalization.

5.3 Study Population

Participants with type 2 diabetes who are admitted to Boston Medical Center and who meet eligibility criteria.

5.3.1 Number of Participants

We anticipate that we will need to screen (consent) 210 patients to randomize 89 participants per group in order to achieve a sample size of 80 participants per group (expecting a 15% screen fail rate and a 10% rate of drop out or early hospital discharge). See section 6.7.3 for detailed power calcuations.

5.3.2 Eligibility Criteria/Vulnerable Populations

Participant eligibility should be reviewed and documented by an appropriately qualified member of the Investigator's study team before subjects are included in the study.

Participants must meet all of the following inclusion criteria to be eligible for enrollment into the study:

Inclusion criteria:

1. English-speaking or Spanish-speaking

- 2. Males and female adult subjects admitted to Boston Medical Center to a medical or surgical floor.
- 3. Age ≥21 and <80 years.
- 4. Diagnosed with type 2 diabetes at least 180 days prior to screening.
- Hyperglycemia during admission, as defined by a point of care and/or venous blood glucose ≥ 140 mg/dL.
- 6. Prior to admission subjects must be using one of the following for outpatient diabetes management:
 - a. Insulin
 - b. \geq 2 oral/injectable agents
 - c. One oral/injectable agent with a HbA1c of \geq 8% within 3 months of enrollment.
- 7. Patients who are expected to remain hospitalized for a minimum of 48 hours following CGM placement.
- 8. BMI <45 kg/m².
- 9. Subjects must have insulin glargine dosing planned at bedtime for the duration of the study period. Morning and afternoon dosing of insulin glargine are exclusionary.

Participant candidates must not be enrolled in the study if they meet any of the following criteria:

Exclusion criteria:

- 1. Patients with a history of type 1 diabetes or late-onset autoimmune diabetes (LADA).
- 2. Currently on glucocorticoids OR plan for treatment with glucocorticoids within the next 72 hours.
- 3. Female patients who are pregnant (tested during hospitalization or screening) or breastfeeding during the hospitalization.
- 4. Patients admitted with the following conditions: diabetic ketoacidosis, hyperosmolar hyperglycemic state, solid organ transplantation, or coronary artery bypass surgery.
- 5. Prior diagnosis of gastroparesis or cirrhosis.
- Acute or chronic kidney disease with a serum creatinine of ≥ 2 mg/dL at the time of screening.
- 7. Clinically significant nausea and/or vomiting or unable to consume more than 30 grams of carbohydrate at each meal.
- 8. Patients expected to receive nothing by mouth (NPO) for >24 hours.
- 9. Use of continuous or intermittent enteral feeding or parenteral nutrition.
- 10. Patients receiving > 1 gram every 6 hours of acetaminophen (maximum dose of acetaminophen) and/or hydroxyurea during the hospitalization.
- 11. Any psychiatric condition rendering the subject unable to provide informed consent.
- 12. Patients currently incarcerated.

- 13. Patients using >1 unit/kg/day of insulin prior to admission.
- 14. Insulin pump usage within the 2 weeks prior to or during admission.
- 15. Patients currently using real-time continuous glucose monitoring (CGM) or personal flash glucose monitoring (FGM).
- 16. Patients with a history of an allergy to any of the types of insulin or one of the excipients in the insulin used in the study.
- 17. Patients who have tested positive for SARS-CoV-2 (severe acute respiratory syndrome coronavirus 2) in the past 30 days OR there is an ongoing clinical suspicion for COVID-19 infection.

Women of childbearing potential: A negative urine pregnancy test is required for all women of childbearing potential at screening, if one has not already been performed during the current hospitalization. Women in the postmenopausal state (defined as no regular menstrual bleeding for at least 1 year), women who have had their uterus removed (hysterectomy), both of their ovaries removed (bilateral oophorectomy), or who have undergone a bilateral tubal ligation are considered not of childbearing potential.

6 – Methods

6.1 Method of Assignment/Randomization

This is an open-label, 1:1 randomized trial. Treatment assigned will be determined by the study team through computer-generated randomization.

6.2 Assessments

The following assessments will be completed during the study:

Medical History: Study staff will obtain a prior history of diabetes and outpatient diabetes treatment medications. For women of non-childbearing potential, the reason should be documented.

Demographic/Medical information: Age, sex, BMI, vitals and reason for hospitalization will be obtained from the medical chart. Patients will be asked their self-identified race/ethnicity (white, black, Hispanic/Latino, Asian, or other). The most recent HbA1c if obtained during the index hospitalization or within 3 months prior to hospitalization will be collected from the medical chart. The serum creatinine at the time of randomization will be collected from the hospital record (note: serum creatinine is routinely obtained on all individuals admitted for inpatient care as part of the standard of care).

Blood Glucose Values/use of CGM: For insulin adjustment and treatment and monitoring of hypoglycemia, the standard hospital point of care meter will be used. At randomization a Dexcom G6 Pro CGM will be placed by the study team on the skin of the upper arm of the subject to collect blinded SG data during the study. The tiny sensor is under the skin and measures the interstitial glucose level, which is the glucose found in the fluid between the cells. The CGM device will be removed at the end of the study and the SG data from CGM will be used to assess glycemic outcomes.

If at any time the CGM becomes dislodged, a new device will be placed by the study team as soon as possible. If the patient must undergo a test during the study such as a CT scan or MRI where the CGM cannot be worn, the study team will remove the CGM prior to the test and place a new one as soon as possible immediately after the test.

Patient Reported Outcome (PRO) questionnaire: Study subjects will be asked to complete a questionnaire at the completion of the study (after sensor removal and before discharge). This questionnaire will assess the subject's perception of wearing a CGM device in the hospital and will also screen for adverse effects from wearing the CGM.

